3.4 DLT Definition

DLT is defined as clinically significant non-hematologic adverse event or abnormal laboratory value assessed as unrelated to disease progression, intercurrent illness, or concomitant medications and occurring during the first cycle (28 days) on study that meets any of the following criteria:

- CTCAE Grade 3 AST (SGOT) or ALT (SGPT) for $>/= 7$ days or grade 3 hyperbilirubinemia for $>/= 7$ days

- CTCAE Grade 3 AST (SGOT) or ALT (SGPT) accompanied by grade 2 bilirubin increase
- CTCAE Grade 4 AST (SGOT) or ALT (SGPT) of any duration
- All other clinically significant non-hematological adverse event that is Grade 3 or 4 according to the NCI common terminology criteria version 4.0 with the following exceptions:
 - Grade 3 or 4 nausea, vomiting and diarrhea will be considered DLT only if not controlled by optimal therapy within 72 hours.
 - Grade 3 biochemical abnormalities (e.g., lipase or bilirubin elevation) will only be considered DLT if accompanied by clinical consequences. Grade 3 or 4 electrolyte abnormalities will only be considered DLT if possibly related to study drug and not corrected by optimal replacement therapy within 72 hours.
- Results in discontinuation of therapy
- Any treatment-related death;

Grade 4 neutopenia lasting \geq 42 days from start of cycle in absence of evidence of active AML.

For patients in venetoclax-containing arms (i.e. Arms B and D) who do not receive venetoclax on day 1 due to logistical and/or financial reasons, the DLT period will be extended to 28 days from the first dose of venetoclax. For evaluation of neutropenia-related DLT, the DLT period will be 42 days from the first dose of venetoclax. Evaluation of the first 6 patients in each of the venetoclax containing treatment arms (arms B and D) will occur after all patients have completed two cycles of treatment (or at least 56 days from the first dose of venetoclax). Enrollment will be halted while the first 6 patients in each of these treatment arms are evaluated for safety.

Please see statistics section (section 11.0) for efficacy and toxicity stopping rules to be applied independently to each cohort.

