Evaluation of the first 6 patients in each treatment arm will occur after all patients have completed two cycles of treatment (or at least 56 days from the first day of treatment). Enrollment will be halted while the first 6 patients in each treatment arm are evaluated for safety. The treatment combination will be considered as safe, and continue to enroll to a total of 21 patients (Arms E-F) or 24 patients (Arms C-D) or 30 patients (Arm B) when there are no more than 1 out of 6 patients with DLTs in the first cycle of treatment. If any patients in the first 6 of each treatment arm withdraw from the study without a DLT event prior to completing the first cycle of treatment, they will be replaced for the assessment of DLT rate. This will allow for early identification of significant toxicities and early stoppage in potentially toxic arms. If 2 or more out of 6 patients have DLTs in the first cycle of treatment in any arm, then an additional 6 patients will enroll at a next lower dose level to be determined by the PI, sponsor (MDACC IND office), and Pfizer team after reviewing the safety, efficacy, and PD data from the first 6 patients enrolled. If no more than 1 out of the additional 6 patients treated with the lower dose level experience DLTs, this treatment combination will be considered as safe and continue to enroll to a total of 21 patients (Arms E-F) or 24 patients (Arms C-D) or 30 patients (Arm B). If 2 or more out of these 6 additional patients experienced DLTs, then this arm will be halted.

The Investigator is responsible for completing the cohort summary template and submitting to the IND office Medical Monitor for review and approval prior to continuing accrual beyond each set of 6 patients in each arm of the study. A copy of the cohort summary should be placed in the Investigator's Regulatory Binder under "sponsor correspondence". This should be submitted after the first six patients.

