5.3 TREATMENT CYCLES

- One cycle of therapy is defined as 28 days (+/- 4 days). Patients will receive one cycle of therapy every 28 days (+/- 4 days).
- Cycles may be started early (but not earlier than day 24) for patients with active disease if judged in the best interest of the patient.
For the dose finding PF-04518600 monotherapy cohort, the DLT defining period is 28 days. As such, cycle 2 should not be commenced before 28 days for the patients being treated in the lead-in cohort.
- Subsequent cycles may be delayed for recovery of toxicity or other medical conditions (e.g. infections). Delays in the start of subsequent cycles greater than 8 weeks will be acceptable only for patients who are deriving clinical benefit and after discussion with the principal investigator of potential risk/benefit ratio and clear documentation in the medical record of the reason for continuation and perceived benefit to the patient from continuation of this therapy.
- In instances where one drug has to be discontinued transiently because of safety, the administration of the other drug/s may continue as scheduled.
- Therapy will be held during phase II of the study, for grade 4 neutropenia or grade 4 thrombocytopenia lasting \geq 42 days from the start of each cycle, in the absence of any evidence of active AML in the bone marrow or peripheral blood. Delays in start of subsequent cycles greater than 42 days will be acceptable only for patients who are deriving clinical benefit and after discussion with the principal investigator of potential risk/benefit ratio.
- If the peripheral counts do not recover (ANC $<0.5 \times 10^9/L$ and/or platelets $<25 \times 10^9/L$) but there is evidence of residual leukemia by morphology or flow-cytometry in the bone marrow, subsequent cycles can be administered at the discretion of the treating physician not earlier than 24 days after the prior cycle in

the phase II portion of the study.

- For patients who discontinue therapy, the reason for treatment discontinuation will be captured.

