The treatment combination will be considered as safe and continue to enroll a total of 30 patients (arm B) or 24 patients (arms C-D) or 15 patients (arms E-F) when there are no more than 1 out of 6 patients with DLTs in the first cycle (28 days) of treatment. If any patients in the first 6 of each treatment arm withdraw from the study without a DLT event prior to completing the first cycle of treatment, they will be replaced for the assessment of DLT rate. This will allow for early identification of significant toxicities and early stoppage in potentially toxic arms. If 2 or more out of 6 patients with DLTs in the first cycle of treatment, then additional 6 patients will enroll at a lower dose level. If no more than 1 out of the additional 6 patients treated with lower dose level experienced DLTs, this treatment combination will be considered as safe and continue to enroll to a total of 30 patients (arm B), 24 (arms C-D) or 15 patients (arms E-F). If 2 or more out of these 6 additional patients experienced DLTs, then this arm will be halted.

Arm F will be closed at this time to further enrollment due to lack of clinical efficacy and competing options of higher priority at our institution.

Futility Monitoring for Arms B-F

The primary endpoint of Arm B-F is the achievement of composite complete response (CRc) within 3 months of therapy initiation in patients with RR AML. The method of Thall, Simon and Estey (1995) will be used to monitor efficacy and safety. After the lead-in, shiny applications were used to generate the operating characteristics for toxicity and futility monitoring, respectively (<http://qcprlshinypyro.mdanderson.edu/postprobtoxicity/>, <http://qcprlshinypyro.mdanderson.edu/postprobfutility/>).

The historical data suggested a composite complete response (CRc) rate of 30% in patients with R/R AML with a variety of different therapies^{4,110,119-122}, and a target response rate is 45%. The study arm will be stopped early if the data suggest that:

$$\Pr(P_E > P_H + 0.15 \mid \text{data}) < 0.05,$$

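### The 28-day DLT limit conflicts with the listed 42-day neutropenia DLT, which falls outside the written counting rule in Arm C and is ambiguous for on-time venetoclax starters in Arms B and D

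*Combined protocol and SAP*

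**What the plan says.** The opening sentence of section 3.4 sets the type of event, "DLT is defined as clinically significant non-hematologic adverse event or abnormal laboratory value assessed as unrelated to disease progression", and the window, "occurring during the first cycle (28 days) on study that meets any of the following criteria". The same section then lists, as a separate criterion, grade 4 neutropenia persisting for at least "42 days from start of cycle in absence of evidence of active AML".

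A later paragraph of 3.4 deals with Arm B and D patients "who do not receive venetoclax on day 1 due to logistical and/or financial reasons, the DLT period will be extended to 28 days", counted from their first venetoclax dose. It continues: "For evaluation of neutropenia-related DLT, the DLT period will be 42 days from the first dose of venetoclax". No comparable sentence exists for Arm C.

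The lead-in rule in section 11 lets an arm continue if there are "no more than 1 out of 6 patients with DLTs in the first cycle (28 days) of treatment". The parallel rule in section 3.3 refers to the first cycle without a day count. On timing, section 3.3 says "Evaluation of the first 6 patients in each treatment arm will occur after all patients have completed two cycles of treatment"; a minimum of 56 days since treatment began is given as the alternative. It replaces only patients who leave without a DLT before finishing cycle 1.

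The toxicity monitoring part of section 11 defines P_T as the probability of DLT and stops an arm if Pr(P_T > 0.15 | data) > 0.80. It looks at 6 patients and then at every 3.

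**The concern.** The neutropenia criterion cannot be met until 14 days after the general window closes (42 - 28 = 14). Two people applying the current text to the same six patients could therefore reach opposite decisions. One counts the neutropenia because 3.4 lists it. The other leaves it out because section 11 counts only 28-day events.

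This matters because safety is the first primary objective, Arms B to D are the arms left for accrual, and the lead-in threshold is 2 of 6. A single event can decide whether an arm continues as planned or enrols six more patients at a lower dose level. P_T has no definition of its own, so it takes over whatever 3.4 means by a DLT, and the same doubt carries into every later toxicity look. If the event is left out, the error always favours continuation.

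**Working it through.** **1. The passages side by side**

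- General window: 28 days (3.4 opening sentence; section 11 lead-in rule).
- Nominal cycle length: 28 days, plus or minus 4 (section 5.3), so at most 32 days. That is still 42 - 32 = 10 days short.
- Neutropenia criterion: at least 42 days from start of cycle (3.4).
- Neutropenia period: 42 days from first venetoclax dose, in the paragraph on late starters in Arms B and D (3.4). The clock start differs from the line above.
- First safety review: after two cycles or at least 56 days (3.3, 5.2, 11). This reaches day 42, but it fixes when the review takes place, not which events enter the count.
- Replacement: only for departure before cycle 1 is completed (3.3, 11). A patient who leaves between day 28 and day 42 is kept as DLT-free although this criterion could not be assessed.

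**2. The plan's own figures**

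The boundary at n patients is the smallest x for which 1 - F(0.15) > 0.80, where F is the Beta(0.3 + x, 1.7 + n - x) distribution function.

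- n = 6: x = 1 gives 0.450 and x = 2 gives 0.801, so the boundary is 2.
- n = 9, 12, 15, 18, 21: x = 3, 4, 4, 5, 5 give 0.873, 0.916, 0.839, 0.890, 0.820. One event fewer gives 0.642, 0.762, 0.639, 0.745, 0.641.

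All printed toxicity boundaries are reproduced. An exact binomial recursion over the looks, with the tables' maxima of 24 (Arm B), 18 (C-D) and 15 (E-F), gives these early-stopping probabilities at a true rate of 0.15:

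| Arms | Recomputed | Printed |
|---|---|---|
| B | 0.345 | 0.342 |
| C-D | 0.302 | 0.290 |
| E-F | 0.259 | 0.264 |

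The largest gap over the 18 tabulated probabilities is 0.012. The printed numbers are sound; the open question is which events feed them.

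**3. Illustration of size**

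Assumptions, none of them from the documents: other DLTs occur at 15%, the neutropenia event occurs with probability q = 5%, 10% or 15%, and the two are independent.

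- Combined rate: p = 1 - 0.85 x (1 - q).
- Passing the lead-in: P(at most 1 of 6) = (1 - p)^6 + 6p(1 - p)^5.
- Not counted, p = 0.15: 0.377 + 0.399 = 0.776.
- Counted, q = 10%: p = 1 - 0.85 x 0.90 = 0.235, giving 0.200 + 0.369 = 0.570 (rounded from unrounded terms).

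| Neutropenia | p | Pass lead-in | Arm B early stop | Arms C-D early stop |
|---|---|---|---|---|
| not counted | 0.150 | 0.776 | 0.345 | 0.302 |
| counted, q = 5% | 0.1925 | 0.674 | 0.525 | 0.454 |
| counted, q = 10% | 0.235 | 0.570 | 0.688 | 0.600 |
| counted, q = 15% | 0.2775 | 0.470 | 0.814 | 0.726 |

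The not-counted row supposes that no such event is counted in any patient. That is the literal reading for Arm C. For Arms B and D it is the extreme case, because late venetoclax starters have an explicit 42-day period.

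**The case against.** A reader might infer that the neutropenia DLT can never be counted. The documents do not support that.

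- Section 3.4 gives an explicit 42-day neutropenia period for at least the late venetoclax starters in Arms B and D. The sentence could be read as covering all patients in those arms.
- The criterion is a separate, specific line, and one may argue that it overrides the general opening sentence. Section 10.1 expects that prolonged myelosuppression can meet the DLT definition, so the intent to count it is plain.
- The opening sentence covers abnormal laboratory values as well as non-hematologic events, so the restriction by event type is a weaker argument than the time limit.
- The 28-day figure is in the section 11 lead-in rule but not in the section 3.3 rule.
- Section 5.2 can be read as asking for two completed cycles at each later look of three patients, not only at the first six.

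A reader might also point to section 5.3, "Cycles may be started early (but not earlier than day 24) for patients with active disease", as cutting the observation short. That provision concerns patients with active disease, and the neutropenia criterion requires that there be none. It therefore does not bear on this event.

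These points show intent and narrow the problem. They do not remove it. Intent in 10.1 does not alter the counting rule in section 11, a late review does not say that late events count, and nothing gives Arm C a 42-day window.

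**Conclusion.** The conflict is real. The 28-day limit in the 3.4 opening sentence and in the section 11 lead-in rule cannot contain a DLT that needs 42 days. The event falls outside the written counting rule in Arm C. Its counting is ambiguous for Arm B and D patients who start venetoclax on day 1, and settled only for late starters in those arms.

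Applied literally, section 11 drops a listed DLT from a 2-of-6 decision. Under the stated assumptions this raises the chance of passing the lead-in from 0.67-0.47 to 0.78. The direction holds for any positive neutropenia rate. The amount depends on an assumed rate, an assumed 15% for other DLTs and independence; at q = 5% the change is about 0.10 (0.776 - 0.674).

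It does not follow that the printed boundaries or operating characteristics are wrong, or that the event would be ignored in every arm.

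**What to change.** Reconcile sections 3.3, 3.4, 5.2 and 11 (lead-in and toxicity monitoring) as follows.

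- Have the lead-in rule and the posterior rule for P_T count every DLT listed in 3.4 that occurs within a named DLT evaluation period. That period should be at least as long as each event listed in it, with one stated clock start. The sponsor chooses the window.
- State neutropenia as an explicit exception to the 28-day, non-hematologic opening sentence. Deleting the word non-hematologic would go further than reconciliation: it could turn other hematologic events, such as any that lead to discontinuation, into DLTs.
- Say which window applies in Arm C and to on-time venetoclax starters in Arms B and D.
- Align the replacement rule with the evaluation period, and state when a patient becomes DLT-evaluable at each look of three.

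The cost is protocol wording, possibly about two weeks more at later looks (42 - 28 = 14 days), and possible replacement of lead-in patients who leave before the period ends. The stopping boundaries need no change.

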- One cycle of therapy is defined as 28 days (+/- 4 days) or 4 weeks. Patients will receive one cycle of therapy every 28 days (+/- 4 days). During the DLT evaluation period the cycle must be a minimum 28 days.

(B) Arm B (Azacitidine + venetoclax + GO in RR AML): N= Up to 26

- Azacitidine will be administered subcutaneously (SQ) or intravenously (IV) for the first 7 days of every cycle with daily schedule of 7 consecutive days (Days 1-7) or for days 5-2-2 which is 5 consecutive weekdays (Days 1-5) with rest on the 2 weekend days (Days 6 and 7) and then dosing the first two weekdays of the next week (Days 8 and 9) of each 28-day cycle (+/- 4 days) as determined by treating physician. Both SQ and IV forms of administration are FDA approved and considered interchangeable. Patients may start receiving azacitidine by one route and changed to the other, and also administration schedules from one schedule and changed to the other at any time as needed based on patient and/or physician preference.

- Venetoclax will be given orally on days 1-28 of cycle 1 and days 1-21 of subsequent cycles. During cycle 1, venetoclax will be dose escalated daily to the goal dose of 400mg daily. Patients will receive 100mg on day 1, 200mg on day 2 and 400mg on day 3 and onwards. This dosing applies to patients in both Phase I and II components of this study.

To minimize the risk of tumor lysis syndrome (TLS), All patients will be hospitalized for the entirety of the venetoclax dose escalation starting at least on day -1 of treatment initiation and until 24 hours after the completion of venetoclax dose escalation. To mitigate the risk for TLS, subjects must be receiving tumor lysis prophylaxis, including hydration (oral, intravenous) and treatment with a uric acid reducing agent (allopurinol, rasburicase) prior to and during the venetoclax ramp up period of Cycle 1. Physicians should leukoreduce with hydroxyurea to reduce the peripheral white blood count to below 15,000/ μ L prior to the administration of the first dose of venetoclax. If the WBC is $>15,000/\mu$ L the venetoclax should not be initiated till the white count is brought down to below 15,000/ μ L

As venetoclax is obtained commercially, some patients may have delays in beginning venetoclax due to financial or other logistical considerations. Even if venetoclax is not yet available, patients may begin azacitidine on day 1.

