- Venetoclax will be given orally on days 1-28 of cycle 1 and on days 1-21 of subsequent cycles. During cycle 1, venetoclax will be dose escalated daily to the goal dose of 400mg daily. Patients will receive 100mg on day 1, 200mg on day 2 and 400mg on day 3 and onwards. Prevention of TLS and need for day 21 bone marrow aspiration in cycle 1 to decide on continued venetoclax administration will be as outlined in Arm B. This dosing applies to patients in both Phase I and II components of this study.

As venetoclax is obtained commercially, some patients may have delays in beginning venetoclax due to financial or other logistical considerations. Even if venetoclax is not yet available, patients may begin the combination of azacitidine and avelumab on day 1. Venetoclax should be started when it is obtained and continued as above (i.e. through day 28). Failure to begin venetoclax on day 1 will not be considered a protocol deviation.

- Avelumab infusion at a dose of 10 mg/kg should begin 30-60 minutes after the completion of azacitidine on day 1, as described above, whenever possible. A second dose of avelumab will be administered on Day 14 of each 28-day cycle.
- Following completion of the infusions, it is recommended to observe patients for 2 hours post-infusion for potential infusion-related reactions. The ambulatory treatment center/inpatient nurse will use the institutional flowsheet to document observation of the patient as per institutional standards.

(E) Arm E (Azacitidine + avelumab + PF-04518600 in RR AML): N= Up to 21

- Azacitidine will be administered subcutaneously (SQ) or intravenously (IV) for the first 7 days of every cycle with daily schedule of 7 consecutive days (Days 1-7) or for days 5-2-2 which is 5 consecutive weekdays (Days 1-5) with rest on the 2 weekend days (Days 6 and 7) and then dosing the first two weekdays of the next week (Days 8 and 9) of each 28-day cycle (+/- 4 days) as determined by treating physician. Both SQ and IV forms of administration are FDA approved and considered interchangeable. Patients may start receiving azacitidine by one route and changed to the other, and also administration schedules from one schedule and changed to the other at any time as needed based on patient and/or physician preference.

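### The DLT window follows a late venetoclax start only for supply or cost delays, not for the protocol's own white-count hold, so some lead-in patients may be judged on less than 28 days of venetoclax

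*Combined protocol and SAP*

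**What the plan says.** - **Default window (3.4).** A DLT is a qualifying event "occurring during the first cycle (28 days) on study".
- **Extension (3.4, Arms B and D).** For patients "who do not receive venetoclax on day 1 due to logistical and/or financial reasons, the DLT period will be extended to 28 days", counted from first venetoclax. The next sentence reads "For evaluation of neutropenia-related DLT, the DLT period will be 42 days from the first dose of venetoclax" and restates no reason for the delay.
- **White-count hold (5.2, Arm B).** Above 15,000/µL, "the venetoclax should not be initiated till the white count is brought down to below" that level. No maximum length of hold is given. Arm D takes this over by reference: "Prevention of TLS and need for day 21 bone marrow aspiration in cycle 1" are to follow Arm B.
- **Starting without venetoclax (5.2).** In the paragraph on financial and logistical delays, Arm B says "Even if venetoclax is not yet available, patients may begin azacitidine on day 1". Arm D has the parallel permission for azacitidine plus avelumab. Neither arm says whether this applies during a white-count hold.
- **Decision rule.** Section 11 calls the combination safe "when there are no more than 1 out of 6 patients with DLTs in the first cycle (28 days) of treatment". Section 3.3 has the same rule for the first cycle. Neither mentions the venetoclax extension.
- **Replacement (3.3 and Section 11).** Only patients who withdraw without a DLT before completing cycle 1 are replaced. No minimum venetoclax exposure is required.

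**The concern.** Section 3.4 accepts the principle that a late venetoclax start leaves too little triplet observation in a window counted from day 1. It then applies the principle to two causes of delay and omits a third that the protocol itself imposes.

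Suppose the backbone begins while venetoclax is held. An event on day 30 would be a DLT for a patient delayed by supply, but not for one delayed equally long by white count. The second patient is not replaced and enters the count of six as a patient without a DLT. The rule turns on a single event (1 of 6 clears, 2 of 6 does not), so one uncounted DLT can decide whether the arm expands at the starting doses. The later toxicity looks use the same DLT definition and inherit the undercount.

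**Working it through.** **1. The plan's own rule.** Section 11 uses a beta(0.3, 1.7) prior and stops if Pr(P_T > 0.15 | data) > 0.80. With 2 DLTs in 6 the posterior is beta(2.3, 5.7), which gives 0.801. With 1 in 6 it is beta(1.3, 6.7), which gives 0.450. The tabulated boundary of 2 at n = 6 therefore reproduces, as do the later Arm B boundaries (3 at 9, 4 at 12, 4 at 15, 5 at 18, 5 at 21). Exact stopping probabilities are within 2 points of the tables (Arm B at a rate of 0.30: 0.864 against the stated 0.856). No stated figure is wrong on this point.

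**2. Clearing the lead-in with full windows.** P(at most 1 of 6) = (1−p)^6 + 6p(1−p)^5. At p = 0.30 this is 0.1176 + 0.3025 = 0.420. At 0.15 it is 0.776, and at 0.40 it is 0.233.

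**3. A shortened window.** The following are assumptions and are not in the documents: constant DLT hazard, a delay of d days with the backbone started on day 1, and the number of patients delayed.

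- All hazard from venetoclax: q = 1 − (1−p)^((28−d)/28).
- Half the hazard from the backbone, which stays fully observed: q = 1 − (1−p)^(0.5 + 0.5(28−d)/28).

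At p = 0.30:

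| Delay d (days) | Venetoclax days observed | q, all venetoclax | q, half backbone |
|---|---|---|---|
| 3 | 25 | 0.273 | not computed |
| 7 | 21 | 0.235 | 1 − 0.7^0.875 = 0.268 |
| 14 | 14 | 0.163 | 1 − 0.7^0.75 = 0.235 |

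**4. Clearing the lead-in with k of 6 delayed.** Let D0 = (1−q)^k (1−p)^(6−k). Then P(clear) = D0 × [1 + kq/(1−q) + (6−k)p/(1−p)].

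Worked case, k = 2, d = 14, all venetoclax: D0 = 0.7 × 0.2401 = 0.168, and P = 0.168 × (1 + 0.390 + 1.714) = 0.522.

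| Patients delayed | Delay (days) | All venetoclax | Half backbone |
|---|---|---|---|
| 0 | – | 0.420 | 0.420 |
| 1 | 3 | 0.430 | not computed |
| 2 | 7 | 0.468 | 0.443 |
| 2 | 14 | 0.522 | 0.468 |

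For other true rates with 2 delayed by 7 or 14 days, all venetoclax: at 0.15, 0.776 becomes 0.804 or 0.832. At 0.40, 0.233 becomes 0.277 or 0.330.

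**5. Does another provision close the gap?** Sections 3.4 and 5.2 time the review of the first six at two cycles or at least 56 days from first venetoclax, whatever the reason for delay. That sets when the data are seen, not which events count. Sections 3.3 and 11 count the 56 days from the start of treatment.

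**The case against.** The strongest objection is that the scenario may not arise. The permission to begin without venetoclax is written for unavailable drug. Section 5.2 asks for leukoreduction before the first venetoclax dose, schedules that dose on day 1 with admission from day −1, and Section 4.1.8 allows hydroxyurea before study therapy. One coherent reading is that the count is lowered before day 1, so the window is never shortened. This stands as a limit. A reader might infer that white-count patients are in fact being cleared on short exposure, and the documents do not establish that. They do not exclude it either: the hold is tied to venetoclax and not to day 1, Section 5.6 allows hydroxyurea during treatment, and Section 4 sets no white-count ceiling for entry.

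Three other stronger readings are not supported.

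- **Tumour lysis events drop out of the count.** They do not for delays of this length. The ramp-up would fall on about days 8–10 after a 7-day delay, or days 15–17 after a 14-day delay. Both are inside day 28.
- **The neutropenia clock also stays at day 1.** The 42-day sentence names no reason and can be read as covering every venetoclax patient. The gap is therefore clearest for non-hematologic DLTs.
- **Section 11 contradicts 3.4.** Section 11 counts DLTs, a term that 3.4 defines along with the specific exception. It is mainly a general wording that lacks a cross-reference.

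There are also real safeguards: Medical Monitor approval after the first six (3.3), stopping or de-escalation above 30% grade 3/4 drug-related toxicity (3.5), capture of grade 3–4 events regardless of attribution (10.1), and toxicity looks every three patients (Section 11). Reviewers would probably see a day-30 event. Under the counting rule, however, it would still not be a DLT.

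**Conclusion.** The gap in the wording is real. The extension is limited to logistical and financial delays, the protocol imposes another cause of delay, and nothing extends the window or makes such a patient non-evaluable. Its effect is conditional on the backbone starting during a white-count hold.

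At an assumed 30% true rate with 2 of 6 delayed by 7 or 14 days, clearance rises by about 5 or 10 points if all hazard is from venetoclax, and by about 2 or 5 points if half is from the backbone. One patient delayed by 3 days adds about 1 point. The all-venetoclax figures are the upper end, because azacitidine, GO in Arm B and avelumab in Arm D also contribute DLTs that remain observed. The documents give neither delay lengths nor the number of patients affected, so these figures illustrate and do not estimate. The point justifies a wording change; it does not undermine the design.

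**What to change.** 1. In 3.4, delete the restriction to logistical and financial reasons. Any Arm B or D patient who starts venetoclax after day 1 is then observed for DLT from day 1 until 28 days after the first venetoclax dose, and until 42 days after it for neutropenia.
2. In 3.3 and the Section 11 lead-in rule, replace the first-cycle wording with a reference to the DLT period in 3.4.
3. Reconcile 3.4 and 5.2 on whether a white-count hold postpones day 1 itself or only venetoclax.

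The cost is wording in a few places, with no change to any dose, white-count threshold or treatment rule. The window for a patient delayed by 7 or 14 days becomes 28 + 7 = 35 or 28 + 14 = 42 days from day 1. More backbone time, and possibly a slightly higher DLT count, is then judged against the same 1-of-6 rule. Little or no extra waiting should follow, because the 56-day review in 3.4 and 5.2 can already run from the first venetoclax dose and the longest window ends 42 days after that dose.
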